5.2 Procedures during Treatment

After the baseline testing is completed, subjects will begin 18 sessions of PT training in the outpatient clinic with a licensed RIC clinical PT. These sessions will last from 45 to 60 minutes. Their sessions will be recorded in RIC's electronic documentation system Cerner.

A blinded research physical therapist will test the outcome measure at baseline, Mid Testing after Session 9, at Post Testing after Session 18 and at 3 month follow up testing after Session 18.

IPT group	Baseline TMS	Baseline testing (blinded PT)	Sessions 1-9 3 x wk	Mid Testing (blinded PT)	Sessions 10-18 3 x wk	Post testing TMS	Post testing (blinded PT)	Follow up testing (blinded PT) 3 months post
SMA group	Baseline TMS	Baseline testing (blinded PT)	Sessions 1-9 3 x wk	Mid Testing (blinded PT)	Sessions 10-18 3 x wk	Post testing TMS	Post testing (blinded PT)	Follow up testing (blinded PT) 3 months post

The TMS protocol

We will test descending corticospinal drive to the rectus femoris, vastus lateralis, lateral hamstrings, tibialis anterior, and medial gastrocnemius muscles. These muscles have the biggest representation in the motor cortex and are most involved during the gait cycle.

Maximum Voluntary Isometric Contractions (MVIC): Before beginning the TMS protocol, an estimate of MVIC will be obtained for each muscle with the subject positioned in sitting on a chair, with the knee joint at 90 degrees of flexion and ankle in neutral position. Manual resistance will be provided by one of the investigators as the subject tries to extend or flex the knee, dorsiflex or plantarflex the ankle. Subjects will then be seated with the feet constrained by flexible 4.0 kg weights placed over the dorsum of each foot. The subject will be given real time feedback of muscle activity to match a target contraction corresponding to 10% MVIC for individual muscles during TMS measurements (details below).

Transcranial Magnetic Stimulation (TMS): TMS is a safe, non-invasive, painless method of brain stimulation that has been widely used to study the physiology of the representations of muscles in the motor cortex in healthy and neurologically disordered individuals¹³. Very short duration (< 1 ms) magnetic pulses are applied via an insulated wire coil placed on the intact scalp overlaying the motor cortical area projecting to a target muscle. Each pulse induces a motor evoked potential (MEP) in a target muscle that can be readily monitored by recording Electromyogram EMG from that muscle. A figure-of-eight or double cone coil is typically used to deliver focal magnetic pulses to a number of scalp sites over the cortical area representing a muscle of interest.

Self-adhesive disposable electrodes (Delsys) with an inter-electrode distance of 2 cm will be applied over the muscle bellies of the quadriceps, hamstrings, ankle dorsiflexors and ankle plantarflexors in the lower extremity. A ground electrode will be applied over the patella. Standard skin preparation techniques (light

abrasion and cleansing with alcohol) will be completed prior to application of the electrodes. EMG recordings will be amplified (Delys, Bagnoli EMG), band-pass filtered (10-1000 Hz), and sampled at 5000 Hz. Electromyographic (EMG) activity will be collected from all the muscles bilaterally. Magnetic stimuli will be delivered via a double cone coil/figure of eight connected to a Magstim 200 unit (Magstim Company, Boston MA). The resting and active threshold for TMS will be determined for each subject. TMS measurements will involve generating motor evoked potentials (MEP) for each muscle from two different coil positions – 2cm on either side of the vertex. Motor evoked potentials (MEPs) at intensities ranging from 70 – 140% active threshold will be generated for each muscle from each coil position. A figure-of-eight or double cone coil will be used to deliver focal magnetic pulses. Resting motor threshold for the muscle of interest will be defined as the stimulator output intensity that can elicit motor evoked potentials (MEPs) with peak-to-peak amplitude more than 50 μ V in four out of eight trials. It will be determined by increasing stimulus intensity in steps of 1% stimulator output. Active thresholds will be determined with the same protocol, however with the subject contracting the muscle of interest to about 10% of maximum voluntary contraction. Subjects will receive approximately 100 – 150 pulses of stimulation. These measures will assist the investigator and co-investigators in generating recruitment curves which will help assess the corticospinal excitability of the ipsilateral and contralateral motor cortex to each lower limb muscle.

The sessions of physical therapy will be customized for each individual based on the group they are placed.

For the IPT group:

Balance IPT OG 15 min	Dynamic Gait OG IPT 15 min	Functional Mobility – IPT OG 15 min

Sitting balance
 
 • Reaching • Perturbations 
Progress to standing
 
Change stance:
 
 • Static • Dynamic • Double limb stance • Romberg • Tandem • Semi-tandem • Unilateral Single limb stance 
Change surface:
 
 • Balance board • Foam cushions, half foam roll • Bosu ball • Balance beam • With/without AFO 
Dual Tasking:
 
 • Ball catch • Cognitive tasks • Reading, visual attention • Perturbations 	
Change surface/stance:
 
 • Level surfaces • Over obstacles • Over compliant surfaces • Tandem walk (forwards/backwards) • With/without AFO 
Multidirectional walking:
 
 • Backwards • Sidestepping • Tandem 
Dual tasking:
 
 • Ball catch • Ball bounce • Cognitive tasks 
Other:
 
 • Increased speed • Pivot turn • Balance beam • Perturbations • Increase distance • Assistive device progression • Reduction in physical assist progression 	
 • Sit to stand transition • Functional up right postures • Reaching • Step up and step down • Stairs • Ramps, curbs • Weights/Theraband • Stretches 
To customize the program, the therapist may adjust the time between the Balance, Dynamic Gait & Functional Mobility needs of the patient.

For the SMA group:

Dynamic Functional Gait – SMA OG 45 min	ALL training for both groups will be High Intensity Training	Home Exercise Program

Change surface/stance:
 
 • Level surfaces • Over obstacles • Over compliant surfaces • Tandem walk (forwards/backwards) • With/without AFO Multidirectional walking: • Backwards • Tandem Dual tasking with gait: • Ball catch • Ball bounce • Cognitive tasks Other Gait challenges: • Increased speed, stopping and starting • Pivot turns • Balance beam • Perturbations • Obstacles • Increased distance • Assistive device progression • Reduction in physical assist progression Functional up right postures • Stairs • Ramps, curbs • Outdoors/community 	
 • Intensity: RPE minimum 12 up to 16 on 6-20 RPE scale • Or HR up to 75% of Age predicted max (220-age) • PT will consider Beta blockers and Ca channel blockers for HR 	
 • Will be customized based on same parameters for both groups: on high intensity gait training • Intensity 12-16 RPE or HR 70% APMHR • Frequency & Duration– initially determined by PT according to pt's functional ability • To work towards 45 min/once a day/at 12-15RPE at d/c

Response Criteria / Outcome Measures:

The following outcome measures will be evaluated for both the groups at testing points at baseline, mid-testing, post-testing and follow-up testing.

Clinical Performance Outcome Measures:

1. **6 Minute Walk Test:** The 6MWT measures the distance a subject can walk indoors on a flat, hard surface in a period of 6 minutes, using assistive devices, as necessary. The test is a reliable and valid evaluation of functional exercise capacity and is used as a sub-maximal test of aerobic capacity and endurance. The minimal detectable change distance for people with sub-acute stroke is 60.98 meters.¹⁴
2. **10 Meter Walk Test:** The 10mWT assesses walking speed in meters per second over a short duration. Changes in gait speed that result in a transition to a higher category of ambulation classification resulted in better function and quality of life¹⁵. In the 10mWT, subjects are directed to walk at their self-selected and maximum safe speed with the effects of acceleration and deceleration minimized (by adding 1 meter at the beginning and at the end of the course to isolate the subject's steady state speed). Any assistive device and orthotic should be kept consistent and documented. It should also be documented whether the gait is tested at "preferred walking speed" or "fastest walking speed". The 10mWT has been validated for the stroke population and is accepted as a responsive, functional measurement of the patient's ability to ambulate over short distances such as those typical to a household setting. A small meaningful change for people with stroke is 0.06 meters/second; a substantial meaningful change is 0.14 meters/second¹⁴. A speed of <0.4 and >.08 m/s is an exclusion in the study.
3. **Berg Balance Scale (BBS):** The BBS is a 14-item objective measure designed to assess static balance and fall risk in adult populations and is a well-accepted measure in the stroke literature. The functional activities that are assessed include sitting and standing balance during transfers, altered base of support, reaching, turning, eyes open and closed. Each item is scored from 0 to 4 points. The maximum score is 56 points. A score from 0 to 20 represents balance impairment, 21 to 40 represents acceptable balance, and 41-56 represents good balance. The minimal detectable change score for individuals with acute stroke is 6.9 points¹⁶ and 4.66 points in chronic stroke¹⁷.
4. **5 Times Sit to Stand Test (5xSST):** The 5xSST is used to measure functional lower extremity strength during the transitional movement of sit to stand. The individual is timed in moving from the start position of sitting, arms across chest, in a standard chair without armrests to fully standing five times. The minimal detectable change in individuals with chronic stroke is 3.6 seconds.¹⁸
5. **Gait Analysis:** A quantitative means of assessing gait function in adults post-stroke based on spatiotemporal parameters of gait. The GaitRite® system is an electronic walkway with integrated sensors and is considered a reliable and valid means of assessing gait changes poststroke.
6. **Functional Gait Assessment (FGA):** The FGA is a 10-item test for assessing postural stability during various walking tasks. It includes 7 of the 8 items from the original Dynamic Gait Index, and 3 new items, including "gait with narrow base of support," "ambulating backwards," and "gait with eyes closed." The FGA demonstrates excellent concurrent validity with the Berg Balance Scale for individuals with stroke.¹⁹ The maximum score is 30 points; minimal detectable change for chronic stroke is 4.2 points.²⁰

7. **Fugl-Meyer Assessment of Motor Recovery after Stroke (FMA):** The purpose of the FMA is to evaluate and measure recovery in post-stroke hemiplegic patients. There are five domains assessed on a 3 point ordinal scale from 0-2. "0" is equal to "cannot perform", "1" is equal to "performs partially", and "2" is equal to "performs fully. The domain for lower extremity motor function will be used. It has been found to be reliable and valid in assessing individuals with stroke with a minimal clinically important difference of 10 points for the lower extremity motor scores.²¹

Self-Reported Measures:

8. **Modified Falls Efficacy Scale (mFES):** The mFES is a 14 item self-report survey that assesses an individual's perception of balance and stability during indoor and outdoor activities of daily living. The mFES is a 10 point numerical rating scale with higher scores indicating higher confidence in the performance of the activity.
9. **Activities- specific and Balance Confidence Scale (ABC):** The ABC is a 16-item self-report questionnaire that measures confidence in performing various ambulatory activities without falling. Items are rated on a scale ranging from 0-100, with zero representing no confidence and 100 representing complete confidence. It has good to excellent reliability and adequate construct validity, correlating with the BBS and 10mWT.²²
10. **Stroke Impact Scale (SIS):** The SIS is a validated measure of the impact of stroke on overall physical and cognitive function. This 59-item patient-based questionnaire assesses eight domains of stroke recovery: strength, mobility, communication, emotion, memory and thinking, participation, activities of daily living/instrumental activities of daily living (ADL/IADL) and hand function. An additional question requires the patient to rate their stroke recovery on a scale from 0 to 100. This measure instructs subjects to answer the question based on the period of time two-four weeks prior to the questionnaire.
11. **Community Participation Indicators (CPI):** The CPI is an eighty-item self-report questionnaire that assesses the individual's satisfaction with their community participation.
12. **Visual Analog Scale or Numeric Pain Rating Scale:** The 0-10 rating scale for pain is used to gain a subjective report of the intensity of a person's pain. Zero represents "no pain" and ten represents "the most intense pain imaginable". A meaningful change would be plus or minus 3 points.
13. **Patient Health Questionnaire-9 (PHQ-9):** The PHQ-9 is a 9-item self-report screening assessment for depression. It is the depression module of the Diagnostic and Statistical Manual (4th edition). Each item is scored from 0-3; total scores may be 0-27, with higher scores representing increased severity of depression.
14. **Stroke Specific Quality of Life (SSQoL):** The SSQoL is a self-report questionnaire that is accepted as a reliable and valid way to assess health-related quality of life specific to stroke survivors. Subjects respond to 49 questions in 12 domains: mobility, energy, upper extremity function, work/productivity, mood, self-care, social roles, family roles, vision, language, thinking, and personality. Each item is rated on a 5-point Likert scale, with higher scores indicating better functioning. Domains scores (un-weighted average of item scores) and a summary score (un-weighted average of all 12 domain scores) are computed.

15. **TMS:** will assist researchers in generating recruitment curves which will help assess the corticospinal excitability of the ipsilateral and contralateral motor cortex to each lower limb muscle.

16.

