2.2 Secondary Objectives

- 2.2.1** To determine the effect on functional walking endurance as assessed by the 6 minute walk test, of task specific training with the SMA device vs impairment based physical therapy in an outpatient setting for post stroke individuals.
- 2.2.2** To determine the effect on functional balance, as assessed by the Berg Balance Scale, Functional Gait Assessment and Five times sit to stand measure as assessed by the 6 minute walk test, of task specific training with the SMA device vs. impairment based physical therapy in an outpatient setting for post stroke individuals.
- 2.2.3** To determine the effect on stroke recovery, as assessed by the step counter of task specific training with the SMA device vs. impairment based physical therapy in an outpatient setting for post stroke individuals.
- 2.2.4** To determine the effect on descending corticospinal drive to the lower limb muscles in training with the Stride Management Assist (SMA) device vs. impairment based physical therapy in an outpatient setting for post stroke individuals.

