8.3 Data Analyses Plans

The outcome measures for each subject (listed in Section 5.2) are recorded during 0th, 10th and 18th session of the training cycle and at 3 month follow up visit. Photographs and video without individual subject's faces will be recorded as this device is not commercially available yet and dissemination of accurate information will be assisted by showing how the device operates when donned and used by subjects. Outcome measures are compared with in the subject and across the subject pools for statistical significant differences using Multiple ANOVAs. All the statistics will be performed at 90% confidence level.

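### Objective 2.2.4 rests on up to 20 recruitment curves per session with no curve parameter, muscle or paretic/non-paretic pathway fixed in advance, and the only analysis rule is unadjusted testing at alpha 0.10

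*Combined protocol and SAP*

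**What the plan says.** Section 2.2 sets the objective (2.2.4): "To determine the effect on descending corticospinal drive to the lower limb muscles", SMA against impairment-based therapy.

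The TMS protocol in Section 5.2 lists the "rectus femoris, vastus lateralis, lateral hamstrings, tibialis anterior, and medial gastrocnemius muscles". It then says "Electromyographic (EMG) activity will be collected from all the muscles bilaterally", and that motor evoked potentials are generated "for each muscle from two different coil positions", 2 cm to either side of the vertex. The resulting curves are to "help assess the corticospinal excitability of the ipsilateral and contralateral motor cortex to each lower limb muscle". Item 15 of the outcome list in the same section repeats that description and adds no summary measure.

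Neither the TMS text nor Section 8 mentions the paretic limb, the lesioned hemisphere or the side of stroke. The eligibility criteria in Section 3 do not restrict lesion side.

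Section 8.3 has one rule for all outcomes: "Outcome measures are compared with in the subject and across the subject pools for statistical significant differences using Multiple ANOVAs". It adds "All the statistics will be performed at 90% confidence level". It gives no multiplicity adjustment and no model specific to TMS.

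**The concern.** There are two separate weaknesses in one outcome.

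The first is multiplicity. Many curves bear on one objective, none is chosen to stand for it, and the stated rule is unadjusted testing at 0.10. If the curves are tested one by one, a chance difference in some muscle from some coil position is likely, and it could be reported as a change in corticospinal drive.

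The second is labelling. Cortex contralateral to the muscle is, for a one-sided stroke, the lesioned hemisphere when the muscle is in the paretic leg and the intact hemisphere when it is in the other leg. The ipsilateral/contralateral label therefore does not separate the pathway of interest from its comparator. Nor does a left/right label, in a sample with strokes on either side. Section 1.1 attributes gait deficits partly to reduced corticospinal drive, and Section 1.3 offers enhanced excitability as a possible mechanism of recovery, so this is the distinction the objective needs. If the two pathways are mixed, an effect on the paretic side alone is diluted.

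**Working it through.** The documents give no TMS test count, error rate, effect size or power, so there is no planned figure to reproduce.

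**Inputs from the documents**
- 5 muscles, 2 limbs, 2 coil positions (Section 5.2).
- Alpha 0.10 per test, from the 90% confidence level in Section 8.3. Two-sided testing is assumed because sidedness is not stated.
- 80 enrolled, 40 per arm, with 30% attrition planned (Section 5.1): 40 x 0.70 = 28 per arm.

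**Number of curves**
- 5 x 2 x 2 = 20 per session.
- With the two limbs merged under ipsilateral/contralateral: 5 x 2 = 10.

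**Chance of at least one false arm difference, one test per curve**
- For k independent tests: 1 - (1 - 0.10)^k.
- k = 20: 1 - 0.9^20 = 1 - 0.122 = 0.878. The expected number of false positives is 20 x 0.10 = 2.
- k = 10: 1 - 0.9^10 = 1 - 0.349 = 0.651.
- Curves from one person will be correlated, so equicorrelated two-sided z-tests were simulated (200,000 sets; the correlations are assumptions):

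| Common correlation | 20 tests | 10 tests |
|---|---|---|
| 0 | 88% | 65% |
| 0.3 | 80% | 58% |
| 0.5 | 66% | 49% |
| 0.7 | 48% | 37% |
| 0.9 | 27% | 23% |

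- 88% is not an upper bound. Adding a within-subject test per curve gives 40 tests, and 1 - 0.9^40 = 0.985 if independent. A second parameter per curve would add more.

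**Dilution, as an illustration**

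Assumptions: 28 per arm, an effect of 0.67 SD in the paretic limb and none in the other, half the lesions on each side, two-sided t-test at 0.10.
- Paretic limb analysed as such: standardised effect 0.67, power 80%.
- One limb analysed as left or right: half the subjects carry the effect, so the mean difference is 0.67/2 = 0.335. The variance in the treated arm is 1 + 0.67²/4 = 1.112, the pooled SD is √((1 + 1.112)/2) = 1.028, and the standardised effect is 0.335/1.028 = 0.326. Power is 33%.
- Each subject's two limbs averaged: the mean difference is again 0.335, with SD √((1 + r)/2) for between-limb correlation r. The standardised effect is 0.474, 0.387 and 0.363 at r = 0, 0.5 and 0.7. Power is 54%, 42% and 38%.

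**What each part of the remedy does**
- Paretic labels with 20 tests still run at 0.10: 87.8%, unchanged.
- One pre-specified TMS test at 0.10: 10%.
- For comparison, Bonferroni over 20 (0.10/20 = 0.005 each): 1 - 0.995^20 = 9.5%.

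**The case against.** The strongest reply is that the plan is silent here rather than wrong. Section 8.3 does not say that each curve is tested separately, and TMS is one item in the outcome list. Nothing says that limbs are pooled or analysed as left and right. Bilateral recording keeps the limbs separable, so lesion side can still be used at analysis. All of this stands, and it is why both sets of figures are conditional. It does not remove the problem: a pathway, muscle and parameter chosen after the data are seen is exactly the freedom that pre-specification should close.

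A reader might also infer that the missing paretic label causes the 88%. It does not. That figure comes only from 20 unadjusted tests and would be the same with perfect labels. Mixing pathways costs power and clarity; it does not by itself raise the false-positive rate. The two worst cases, 20 tests and mixed pathways, also occur together only under left/right labelling, which the plan never states.

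The dilution figures rest on an assumed effect size, on the effect being confined to one limb and on an even split of lesion sides. The fall from 80% to 33% is the least favourable reading. If the left and right limbs are both tested, the chance that at least one shows the effect is about 56%, 50% and 46% at between-limb correlation 0, 0.5 and 0.7. The 28 per arm may also be too high for TMS, because Section 3.1 makes TMS conditional on compatibility.

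Finally, unadjusted testing at 0.10 is a feature of Section 8.3 for every outcome. What is particular to TMS is that no single quantity represents the objective.

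**Conclusion.** The concern holds in conditional form. Objective 2.2.4 has up to 20 candidate curves per session and no defined outcome. Applying the stated rule to each curve gives a chance of at least one false arm difference of 88% if independent, 66% at correlation 0.5 and 48% at 0.7. With the limbs merged, it is 65%, 49% and 37%. All of these are well above the nominal 10%.

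As a separate matter, analysing the curves under the plan's labels would dilute an effect confined to the paretic side. On the illustrative assumptions, power falls from 80% to 38-54% if limbs are averaged, or to 33% for a single left or right limb test.

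The documents do not support saying that the plan instructs pooling, that it prescribes 20 separate tests, or that the labelling gap inflates the error rate. TMS serves a secondary objective, and the primary gait-speed test is untouched. The change should be made, but the trial's main conclusion does not depend on it.

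**What to change.** In Sections 5.2 and 8.3:

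1. Label every TMS curve by paretic or non-paretic limb, and by hemisphere relative to the paretic limb. Use side of stroke recorded at baseline, and state a rule for bilateral strokes, which Section 3 does not exclude.
2. Name one curve parameter in advance, for example the area under the recruitment curve.
3. Answer 2.2.4 with one repeated-measures model of the baseline-to-post change in that parameter. It should cover the five paretic-limb muscles evoked from the hemisphere contralateral to the paretic limb, with muscle as the repeated factor and a single arm effect.
4. Report all other curves and single-muscle results as descriptive.

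Items 2 to 4 bring the false-positive chance for the objective back to the 10% that the plan's alpha implies. Item 1 removes the mixing of pathways. Both parts are needed, because neither does the other's work.

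The cost is plan wording and one baseline variable. Section 5.3 already schedules a history and examination at baseline, although it does not list side of stroke by name, so the case report form should. No extra TMS procedure is required. The small downside is that effects in other pathways or in single muscles become exploratory.

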4.4 Removal of Patients from Protocol Therapy

Patients may be removed from therapy if there is a change in medical status. The Principal Investigator may also decide if the patient is unable to continue for any extenuating circumstances to remove the subject from the study, and document the reason for study removal and the date the patient was removed in the Case Report Form.

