5.0 STUDY PROCEDURES

5.1 Screening/Baseline Procedures

Subjects will be randomized into 2 separate groups, either SMA or IPT. We will enroll 80 subjects, 40 in each group, planning for a 30% attrition rate. These subjects will be recruited when they are referred to RIC's stroke rehabilitation outpatient clinics at RIC's flagship at [name], or RIC Northshore in Northbrook IL or RIC Willowbrook in Willowbrook, IL. We will also recruit from local physicians or RIC's Clinical Neuroscience Research Registry for subjects who are potential candidates for outpatient physical therapy. They will be directed to a physical therapist who will inform them of the time commitment required and questioned regarding the inclusion/exclusion criteria. Once subjects have agreed to participate in the study, they will come to RIC and be consented at one of the clinics at the Rehabilitation Institute of Chicago. Study staff will explain the study, a written consent form will be signed by the subject and witnessed by study researchers, a copy will be given to the subject and a copy will be kept in the subject's folder in a secure, locked cabinet in the lab's locked office.

After consenting, subjects will undergo a physical evaluation and screening exam by a licensed PT. If they meet study criteria, they will be randomly placed into either the SMA group or the IPT group using a random number generator and they will be entered into the study. Once they are enrolled, baseline outcome measures will be assessed by a blinded research PT.

In addition, subjects will have a baseline measure of their cortical excitability through TMS. This will be conducted at University of Illinois, Department of Physical Therapy. TMS sessions will last approximately 2 hours.

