5.4 Removal of Subjects from Study

- 5.4.1 Patient voluntarily withdraws from treatment
- 5.4.2 Patient withdraws consent (termination of treatment and follow-up);
- 5.4.3 Patient is unable to comply with protocol requirements
- 5.4.4 Patient demonstrates change in medical condition
- 5.4.5 Patient experiences adverse event that makes continuation in the protocol unsafe;
- 5.4.6 PI judges continuation in the study would not be appropriate;
- 5.4.7 Patient becomes pregnant

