6.0 ADVERSE EVENTS

6.1 Potential risks

6.1.1 The risk of falling: This could be caused by loss of control of the training activity by the participant or therapist as well as malfunction of the SMA device itself. The risk of falling will be minimized by having RIC licensed PT personnel conduct the participant training sessions with manual assistance, gait belt, assistive devices such as cane or a walker as needed. This risk is similar to that during any clinical outpatient physical therapy session.

6.1.2 Discomfort, skin pressure/friction, bruising, pain, or unusual swelling caused by the exoskeleton which has the potential to lead to skin breakdown or abrasions. This risk will be minimized by a thorough skin check performed by RIC's experienced licensed physical therapy personnel at each session. Adjustments to the sizing and placement of

additional padding will be assessed to decrease the risk of skin breakdown as well.

6.1.3 The device itself could malfunction. The device delivers 6-8 Nm (Newton-meter) of torque, which give a gentle assist to movement. In the event of device malfunction, this force will be absent and the subject will be given with physical assistance if required, and the patient will be able to safely transfer out of the device, if required. Research engineers will ensure that the device has been maintained according to specifications and the software is always in working order.

6.1.4 Muscle soreness from exercises during therapy sessions. All subjects will work with RIC's licensed physical therapy personnel and will be initiated with testing and therapy sessions with simple activities, progressing on to more dynamic, complex activities when it is clear that they are safe and acclimated to the protocol being used. To manage this, subject will be provided with adequate rest periods and subjects will be monitored by questions regarding discomfort.

6.1.5 Risks associated with TMS:

There are certain populations who have a risk of seizures following TMS. Individuals will be screened using the TMS safety checklist. Single pulse TMS has been deemed to "carry little risk beyond occasionally causing local discomfort" in healthy adult populations (Anand and Hotson 2002). Our stimulation procedures follow published safety guidelines. Seizure activation is extremely unlikely with the single pulse low numbers of stimulation proposed in the current investigation.

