8.2 Sample Size and Accrual

A total enrollment of 80 subjects is estimated for this study. Each enrolled subject is randomly assigned to either one of the groups (SMA or IPT; 40 participants per group). A detailed description of study procedures and study endpoints are provided in section of 5.0

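### Pain is a named device harm, but the plan compares it only as an arm mean, leaves its own 3-point threshold unused and plans no by-arm summary of removals, so harm can be hidden if harmed subjects are removed or offset by others

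*Combined protocol and SAP*

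**What the plan says.** - **Harms named.** Section 6.1.2 lists "Discomfort, skin pressure/friction, bruising, pain, or unusual swelling caused by the exoskeleton" and says these could lead to skin breakdown. Section 6.1.4 adds muscle soreness. A skin check at each session and questions about discomfort are described as ways to limit or manage these risks.
- **Pain outcome.** Section 5.2, item 12, is a 0-10 pain rating: "A meaningful change would be plus or minus 3 points".
- **Analysis.** Section 8.3: "Outcome measures are compared with in the subject and across the subject pools for statistical significant differences using Multiple ANOVAs". It works at a 90% confidence level. It gives no analysis set, no missing-data rule, no count of subjects who worsen and no safety summary.
- **Removal.** Section 5.4.5 gives as a ground: "Patient experiences adverse event that makes continuation in the protocol unsafe". Sections 5.4.4 and 5.4.6 add a changed medical condition and the investigator's judgement. Under Section 4.4 staff must "document the reason for study removal and the date the patient was removed in the Case Report Form".
- **Session records.** Section 5.2: "Their sessions will be recorded in RIC's electronic documentation system Cerner".
- **Timing of pain scores.** The text of 5.2 puts every listed outcome at baseline, mid-testing, post-testing and follow-up. The table in 5.3 has no mid-testing mark for self-reported measures, the group that holds the pain scale.

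**The concern.** Pain is the only Section 5.2 outcome that directly measures a harm named in 6.1.2, and an arm mean is a poor scale for it. A large rise in a few device wearers can be cancelled by small falls in the rest. A wearer removed because of pain may contribute no later score, so the worst cases can drop out of the comparison.

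What is at stake is the tolerability message. A non-significant mean pain ANOVA, or one that favours SMA, could be read as showing that the device is well tolerated. Section 8.3 says the device is not yet on the market and that information about it will be disseminated, so that message matters. The primary gait-speed comparison is not affected by this point.

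**Working it through.** **Inputs from the protocol.** Section 5.1: "We will enroll 80 subjects, 40 in each group, planning for a 30% attrition rate". That leaves 80 x 0.70 = 56 subjects, 28 per arm. Alpha is 1 - 0.90 = 0.10 (Section 8.3); the sidedness is not stated and two-sided is assumed. The pain threshold is 3 points (item 12). No figure for pain or skin injury is given. The sample size of 80 cannot be reproduced, because Section 8.2 gives no effect size, SD or power.

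**Assumed inputs.** SD of pain change 1.5 (2.5 as a check); a fraction h of SMA subjects with a device-caused 4-point rise; the other SMA subjects unchanged, or improved by c = 0.5 point relative to IPT; a fraction r of the harmed removed without a later score.

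**Expected observed difference, SMA minus IPT:**

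[h(1 - r) x 4 - (1 - h) x c] / (1 - h x r)

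- h = 0.10, c = 0: r = 0 gives 0.40; r = 0.5 gives 0.20/0.95 = 0.21; r = 1 gives 0.
- h = 0.10, c = 0.5: r = 0 gives 0.40 - 0.45 = -0.05; r = 0.5 gives (0.20 - 0.45)/0.95 = -0.26; r = 1 gives -0.45/0.90 = -0.50.
- h = 0.20, c = 0.5, r = 0.5: (0.40 - 0.40)/0.90 = 0.

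**Simulated behaviour of the mean comparison** (40 per arm, 30% random attrition, two-sided t-test at 0.10, SD 1.5; ranges are across repeated runs):

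| Harmed | Others in SMA | Harmed removed | Test says SMA worse | Test says SMA better |
|---|---|---|---|---|
| 10% | no change | none / half / all | 0.20-0.21 / 0.12 / 0.05 | not tabulated |
| 10% | improve 0.5 | none / half / all | 0.03-0.04 / 0.01 / below 0.01 | 0.07 / 0.15-0.16 / 0.31-0.33 |
| 20% | no change | none / all | 0.46-0.47 / 0.05 | not tabulated |
| 20% | improve 0.5 | half | 0.04-0.05 | not tabulated |

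With no true difference, each direction is declared 0.05 of the time. At SD 2.5 the first row becomes 0.14 / 0.09 / 0.05, and the false benefit in the second row under full removal becomes 0.17.

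**Would counting events do better?** Take as an event a rise of 3 or more points or removal for pain, compare arms by Fisher's exact test at 0.10, and count other dropouts as non-events.

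- 10% harmed, no removal, no offset: 0.06 to 0.13, depending on the number of later visits, against 0.20-0.21 for the mean.
- 10% harmed, no removal, offset 0.5: 0.05 to 0.06 against 0.03-0.04.
- 20% harmed, half removed, offset 0.5: about 0.59 at SD 1.5 and 0.30 at SD 2.5, against about 0.05.

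The count is clearly better when harmed subjects are removed and the reason is coded. Otherwise it is no better, or worse, as a test.

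**Precision of a descriptive count.** The exact 90% interval for 4 of 40 is 3.5% to 21.4%. For 0 of 40 the upper limit is 1 - 0.05^(1/40) = 7.2%.

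**Timing.** Under the 5.3 table, a subject removed during the 18 sessions has no scheduled on-treatment pain score. Under the text of 5.2, one removed after mid-testing has one. The two passages lead to different data for the subjects who matter most here.

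**The case against.** **Skin and discomfort data.** A reader might infer that the trial already collects skin-injury data and then ignores them. The documents do not support that. The skin check and the discomfort questions are risk-control steps. The protocol says that sessions are recorded in the clinical system, not that findings are graded, entered or moved to the study data. A blank note could not be told from a negative check. Nor do the documents say that skin injury will go unreported; they contain no plan to report it. This objection stands and limits what can be asked.

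**Who is analysed.** A reader might also infer that the ANOVA is confined to subjects still in the study. No analysis set is stated. Section 5.4 concerns removal from the study, but only 5.4.2 expressly ends follow-up, so some removed subjects might still be scored. The one explicit rule on withdrawal for pain stands under the TMS risks in Section 6.1.5, not the device risks. The loss of scores is therefore a condition, not a fact.

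**Size.** The rates, the SD and the offset are all assumed. With 20% harmed, no removal and no offset, the mean comparison detects harm nearly half the time, and at 10% harmed it outperforms the event count. Other outcomes also carry change thresholds that no analysis uses. This stands too. What remains is that pain is the outcome tied to a named device harm, and that removals have no by-arm summary.

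**Conclusion.** The point holds in a limited form and should be acted on. Section 8.3 compares pain only as a mean, uses the 3-point threshold nowhere, and plans no by-arm account of removals although reasons are recorded. If harmed subjects are removed and give no later score, the mean comparison is biased towards no harm. If the remaining wearers also improve, it is biased towards an apparent benefit.

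Under the assumptions above (SD 1.5, 10% harmed by 4 points), full removal takes detection from about 20% to chance. With a 0.5-point offset as well, a false finding of less pain occurs about 31% to 33% of the time, or 17% at SD 2.5. Without removal or offset the bias is absent and the mean test has no disadvantage in power. The documents do not show that removal for device pain will be common.

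The conflict between the text of 5.2 and the table in 5.3 is independent of these assumptions. It must be reconciled, because it decides whether any on-treatment pain score exists.

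**What to change.** Add to Section 8.3 a descriptive by-arm table of all randomised subjects who attended at least one session, with exact 90% confidence intervals:

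1. The number and percentage with a rise of 3 or more points from baseline on item 12 at any later visit, or removed for a pain, soreness or skin reason. Those removed for such a reason count as events. Subjects who left for other reasons without a later score are shown on their own line and handled by a best-case/worst-case range. For example, with 4 events among 40, and with all 0.30 x 40 = 12 expected dropouts in this group, the range is 4/40 = 10% to 16/40 = 40%.
2. All removals, by reason and arm, from the CRF.

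State that the mean pain ANOVA is not evidence of device tolerability. Report skin-check and session-discomfort findings by arm only as far as the session notes record them, and state that limit. Reconcile Sections 5.2 and 5.3 on pain at mid-testing.

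**Cost.** A few lines of text and some CRF extraction; the table itself needs no new visit or procedure. Removal reasons may be assigned by staff who know the arm, and because they count as events this could tilt the comparison. Intervals will be wide at 40 per arm, so the table should be read as description, not as a formal test.
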